10.3 ANALYSIS OF IOLM COMPONENT

The ability to successfully identify at least one sentinel lymph node in each patient undergoing radical hysterectomy and IOLM will be calculated. In addition, location, number, and laterality of identified sentinel node(s) will be reported. In patients where at least one sentinel node is identified, sensitivity, specificity, positive and negative predictive values of the procedure will be calculated.

10.4 INTERIM ANALYSES AND EARLY STUDY TERMINATION

There is some concern as to whether there may be an increased rate of severe adverse events in the TLRH/TRRH group. The rate of complications will be monitored and formally assessed after 50, 100, 150, 200 and 300 patients randomized into the TLRH group have completed surgery. Early termination will be considered if there are surgery related deaths. The following table gives the upper bound of the number of deaths caused by surgery.

| Number of subjects in | Consider stopping the study if the number |
|-----------------------|-------------------------------------------|
| TLRH/TRRH group | of deaths caused by surgery is ≥ |
| 50 | 2 |
| 100 | 3 |
| 150 | 4 |
| 200 | 5 |
| 300 | 6 |

All toxicity data will be reviewed by a Trial Safety Committee (TSC) (please refer to section 20.1) who will make recommendations to the Trial Management Committee in regards to changes to the protocol and/or stopping the trial. Additional revised power calculations will be undertaken at these times based on both local and total recurrence which may indicate that larger (or smaller) relapse rates may be worth detecting.

Toxicities/complications which will also be considered by the independent Trial Safety Committee (TSC) include:

- a) Conversion to laparotomy as a result of bleeding;
- b) Injury to abdominal or pelvic viscera secondary to endoscopic instrument placement or manipulation. This includes injury to the bowel, bladder, vessels, ureter or kidney;
- c) Development of symptomatic lymphocysts requiring percutaneous drainage or hospitalization;
- d) Nerve injury requiring physical therapy or restricting function;
- e) Unplanned ICU admission.

11.0 ANALYSIS OF COST EFFECTIVENESS

Participation in the economic analysis component is optional for study sites and analyses will be country specific.

11.1 ECONOMIC ANALYSIS

We will assess the cost-effectiveness of the intervention (TLRH \pm Laparoscopic Pelvic/Aortic Lymph Node Dissection) relative to standard treatment alone (TARH \pm Pelvic/Aortic Lymph Node Dissection), calculated as the incremental cost per unit of improvement in functional outcome, and measured in terms of the primary outcome.

The outcomes of this part of the economic analysis will be in terms of costs per disease and treatment specific difference in quality of life at six months. More specifically, costs per fewer days' treatment-related morbidity, shorter hospital stays, less days with post-operative pain, and less analgesic consumption. By assessing the difference in cost between the standard treatment and the proposed intervention, it can be ascertained which of the two treatments represents the most sound investment in terms of the improvement in quality of life.

We will also measure the quality-adjusted life years (QALYs) gained with the intervention and use this to undertake a cost-utility analysis. The QALY calculations will be based on health status measures for trial participants, with valuations of changes in health status and quality of life based on the EQ-5D. Several viewpoints will be considered for the economic analyses, including those of health system purchasers, households and society in general.

This part of the economic analysis allows us to express outcomes in costs per QALY. The aim of this generic outcome measure is to assess whether the study intervention represents value for money as compared to alternative interventions (including for other conditions), and as compared to the various threshold values below which an intervention is considered good value for money (in Australia \$40,000 per QALY is often used).

In terms of measuring costs, a number of components will be considered, including: the intervention costs; the provision of information booklets to patients; GP and specialist consultations; radiology and imaging; prescriptions, over-the-counter medications; community health and social services; days off work; and informal care by family and friends. Direct costs will be obtained for samples of patients, stratified by hospital, operation and outcome, using a bottom-up approach by recording the volume of resource use in both arms of the trial, and then applying a unit cost to each component. Data on all patients' use of healthcare services will be collected using a combination of retrospective

Version 4 October 2014 LACC Trial Page 45 of 105 questionnaires and clinical files. All questionnaires have to be amended to the protocol and approved by the IRB prior to giving to patients. Where possible, local cost tariffs will be used and national sources will be used as comparators.

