5.0 STUDY DESIGN

This Phase III international, multi-centre, open-label, randomized clinical trial design is an equivalence study with the hypothesis that TARH is equivalent TLRH in terms of disease free survival (DFS). The study will be conducted in two stages.

5.1 STAGE 1

The first stage will assess feasibility of recruitment and delivery of the intervention and collect quality of life on the first 100 patients.

5.2 STAGE 2

The Trial Management Committee (refer to Section 19.2) will decide whether the trial will progress along Option 1 or Option 2 based on clinical and economical feasibility and the level of interest amongst the clinical community.

[figure not shown]
Option 1

A randomized equivalence trial with disease-free survival as the endpoint is the definitive means of determining whether TLRH is at least equivalent to TARH. As such, it is planned to extend the trial to a larger randomized equivalence clinical trial (additional 640 patients) assessing disease free survival at 4.5 years from surgery.

Option 2

The study will follow-up the cohort of patients who had received a total laparoscopic or robotic radical hysterectomy for a minimum of 4.5 years post-surgery to determine whether the estimate of disease-free survival for patients who undergo laparoscopic or robotic surgery is consistent with the (control group) four-year disease-free survival rate of 90%.

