7.2 SECONDARY OUTCOME MEASURES

Patterns of recurrence: date and localization of 1st recurrence as confirmed histologically –
 pelvic versus distal.

- Treatment related morbidity, as evaluated by:
 - Intraoperative complications injury to bladder, ureter, bowel; vascular injury and bleeding, nerve injury;
 - Perioperative (time to discharge from hospital): urinary tract infection, urinary retention, ileus, cardiac (myocardial infarction, atrial fibrillation), pulmonary (edema, atelectasis, pneumonia), renal and cerebrovascular morbidity. Wound and vault complications (infection, breakdown, and dehiscence). Septicaemia and thromboembolic complications (DVT, PE). Lymphocyst or abscess formation;
 - Early postoperative (< 4 weeks): Wound and vault complications (infection, dehiscence). Lymphocyst, Abscess formation, Lymphoedema or Fistula formation;
 - Long-term morbidity (4 weeks to 6 months): Lymphoedema, incisional hernia formation, vaginal eviseration.
 - Estimated blood loss: As defined by the total volume of suctioned fluids minus the volumes of irrigation fluids used at the completion of surgery. In addition, blood loss will be reviewed in hemoglobin change from baseline. A Full Blood Count (hemoglobin) will be taken before and the morning after the operation;
 - Postoperative pain and analgesic consumption using pain scores and analgesic consumption measurements;
- Costs: measured as the incremental cost per unit of improvement in functional outcome, measured in terms of the primary outcome plus using quality-adjusted life years (QALYs) to undertake a cost-utility analysis;
- Quality of life: Change in Quality of Life using Functional Assessment of Cancer Therapy Cervical (FACT-Cx), the MD Anderson Symptom Inventory (MDASI, Short Form-12 (SF-12) and EuroQoL-5D (EQ-5D) between Baseline (pre-surgery) and 6 months after surgery.
- Pelvic Floor Distress Inventory: measures symptom severity and quality of life changes in women with pelvic floor disorders. The Pelvic Floor Distress Inventory (PFDI) provides a standardized, reproducible assessment of the patient's symptoms and their effect on daily life⁸⁸.
- Overall survival at 4.5 years follow-up
- Feasibility of sentinel lymph node biopsy in this group of patients.

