- The date of death will be recorded and every effort will be made to obtain a cause of death (possibly disease-related, possibly treatment-related).
- Provide patient with the Pelvic Floor Distress Inventory and FACT-CX at Follow-Up 4, 7, 9 and
 11 these must all be done within 1 month of due date (if not received by patient, this is not considered a deviation from the Protocol).

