15.0 OTHER QUESTIONNAIRES

15.1 HEALTH SERVICES QUESTIONNAIRE (HSQ)

Seven items assessing health care utilization during the past 6 months were adapted from Health Care Utilization items developed by the Stanford Patient Education Research Centre (http://patienteducation.stanford.edu/research/utilization.html). The original items were reported to have to excellent test-retest reliability ranging from 0.76-0.97 and to validly report use of such services⁹⁴. The HSQ will be provided to patients for completion at Post Op Visits 3, 4, 5 and 6.

Version 4 October 2014 LACC Trial Page 51 of 105

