15.2 EuroQoL-5D (EQ-5D)

EQ-5D is a standardized instrument for use as a measure of health outcome. It provides a descriptive profile and a single index value for health status. EQ-5D was originally designed to complement SF-36. EQ-5D will measure changes in health status and quality of life to calculate the quality-adjusted life years (QALYs) gained with the intervention. EQ-5D will be provided to patients for completion at Pre and Post Op Visits 1, 3, 4, 5 and 6.

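### The economic analysis sets two incompatible outcomes and horizons (4.5-year DFS and six-month quality of life), and its only utility measure stops at month 6, before about 88% of expected recurrences

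*Protocol*

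**What the plan says.** Section 7.2 lists among the secondary outcomes "Costs: measured as the incremental cost per unit of improvement in functional outcome, measured in terms of the primary outcome", with a QALY-based cost-utility analysis alongside. Section 11.1 repeats the definition: cost-effectiveness is "calculated as the incremental cost per unit of improvement in functional outcome, and measured in terms of the primary outcome". Section 7.1 sets the primary outcome as DFS at 4.5 years after surgery.

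The second paragraph of 11.1 then states the outcome of this same part of the analysis as "costs per disease and treatment specific difference in quality of life at six months", and spells it out as morbidity days, hospital stay, days in pain and analgesic use. Later paragraphs add cost per QALY from EQ-5D. The aim there is to judge value for money against interventions for other conditions and against a threshold, given for Australia as $40,000 per QALY.

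On data collection, section 15.2 says "EQ-5D will be provided to patients for completion at Pre and Post Op Visits 1, 3, 4, 5 and 6", and section 15.1 says "The HSQ will be provided to patients for completion at Post Op Visits 3, 4, 5 and 6" for the Health Services Questionnaire (HSQ). Visit 6 is the six-month visit, and Appendix 1 has no follow-up entry for either form. By contrast, section 12.4 says "Provide patient with the Pelvic Floor Distress Inventory and FACT-CX at Follow-Up 4, 7, 9 and" 11, which are months 18, 30, 42 and 54.

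**The concern.** The protocol gives one analysis two outcomes with two horizons. Neither a six-month quality-of-life difference nor 4.5-year DFS can stand in for the other, and nothing says which governs.

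If the DFS version is followed, the ratio divides a cost difference by a quantity that the design expects to be zero.

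If the QALY version is followed, the utilities cover recovery from surgery and little else. Section 3.2 cites a randomised comparison of hysterectomy by laparoscopy and laparotomy in which the quality-of-life advantage was short-term and the arms were equivalent by six months. The EQ-5D window thus spans the period in which a minimally invasive approach can be expected to look better. It closes before most of any loss from recurrence would appear, in a trial run because the effect on recurrence is not known.

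At stake is a named secondary objective, the cost-effectiveness comparison, and the general value-for-money statement attached to it.

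**Working it through.** **Inputs.** From section 9.0: control DFS 90% at 4.5 years, exponential survival, 370 per arm, margin 7.2 points, 80% power, 95% confidence. From section 5.0: the hypothesis of equal DFS. From sections 12.3, 15.1, 15.2 and Appendix 1: the last EQ-5D and HSQ at month 6.

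**1. The planned sample size rests on a true difference of zero.** Section 11.1 states no figure of its own, so the check starts from the trial's 740. Equivalence as two one-sided tests at 0.025 each, true difference 0, binary approximation:

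n per arm = (1.960 + 1.282)² × 2 × 0.9 × 0.1 / 0.072² ≈ 365, or 730 in total, 1.4% below 740.

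At 370 per arm, 0.072 / 0.02206 − 1.960 = 1.304, so power = 2 × 0.904 − 1 = 80.8%. The stated 740 at 80% is reproduced, with an expected DFS difference of 0.

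**2. The denominator of a cost-per-DFS ratio.**

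SE = √(2 × 0.9 × 0.1 / 370) = 0.0221, that is 2.2 percentage points around 0.

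For two binomial samples of 370 at 90%, the estimated difference is negative in about 48% of trials, exactly zero in about 5% and positive in the rest. It lies within 1 point of zero in about 33%. As an illustration with an assumed cost difference of $1,000, an estimate of +1 point gives 1,000 / 0.01 = $100,000 per additional disease-free patient, and −1 point gives −$100,000. Both estimates are less than half a standard error from zero.

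**3. Share of recurrences after the last utility measurement.**

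Hazard = −ln(0.90) / 4.5 = 0.02341 per year.

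Recurrence by 0.5 years = 1 − exp(−0.02341 × 0.5) = 1.16%; by 4.5 years, 10%.

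Share after month 6 = 1 − 1.16 / 10 = 88%. In an arm of 370 that is about 33 of 37 recurrences (37 − 4.3 = 32.7). With DFS of 82.8% the share is 1 − 2.08 / 17.2 = 88% again.

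**4. What a six-month window sees of a recurrence penalty.** Suppose DFS were worse by the full margin (82.8%, hazard 0.04194). Mean disease-free time to T is (1 − exp(−hT)) / h.

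| Horizon | 90% DFS | 82.8% DFS | Difference |
|---|---|---|---|
| 0.5 years | 0.4971 | 0.4948 | 0.0023 years |
| 4.5 years | 4.2710 | 4.1008 | 0.1702 years |

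The documents give no utility loss after recurrence. Assuming a range of 0.1 to 0.5, the QALY loss per patient is 0.0002 to 0.0011 over six months and 0.017 to 0.085 over 4.5 years. Whatever the value in that range, six months captures 0.0023 / 0.1702, little over 1%. At $40,000 per QALY the 4.5-year loss is worth about $680 to $3,400 per patient.

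**The case against.** The best defence has four parts.

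First, a reader might infer that service-use data stop at month 6 and that recurrence costs are therefore left out. The documents do not say so. Only the HSQ stops. Section 11.1 also draws service use from clinical files with no stated cut-off, and section 12.4 records the treatment of recurrence and the date of death during follow-up to 4.5 years. Later costs and lost life-years can thus be observed. This part stands. What remains is narrower: recurrence treatment is not among the cost components that 11.1 lists, no horizon commits the analysis to counting it, and utilities after month 6 do not exist.

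Second, a reader might call the cost-per-DFS ratio undefined. It is undefined only at an estimate of exactly zero. Otherwise it is unstable and of either sign. The problem does not touch the six-month quality-of-life outcomes or cost per QALY.

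Third, a reader might conclude that the trial would report an approach with more relapses as good value. That needs a fixed six-month horizon with no extrapolation, which the protocol does not state, and the DFS result would be reported alongside. A larger assumed loss, such as 2 QALYs per recurrence, would be close to death at recurrence, because recurrences spread evenly over 4.5 years leave on average about 2.25 years in the window.

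Fourth, horizon, extrapolation and net benefit are usual content for a later analysis plan. That is fair for method, but such a plan cannot supply utilities that were never collected, and the contradiction lies in the protocol's own text.

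**Conclusion.** The point holds in this form. Sections 7.2 and 11.1 tie cost-effectiveness to 4.5-year DFS, while the next paragraph of 11.1 ties it to six-month quality of life, and these passages must be reconciled. Under the trial's own hypothesis the cost-per-DFS ratio cannot be interpreted, because its denominator has mean 0 and SE about 2.2 points. EQ-5D covers the recovery period but precedes about 88% of expected recurrences, so the measured utilities do not support a general value-for-money comparison with $40,000 per QALY.

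The 2.2 points and the 88% rest on the protocol's planning values: 90% DFS, exponential times, and 370 per arm, which applies only if the trial expands to 740. The QALY and dollar ranges rest on an assumed utility loss and a DFS deficit of 7.2 points, so they illustrate size and do not predict it. The component is secondary and, under section 11.0, optional for sites and country-specific. It should be corrected, but the primary comparison is unaffected.

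**What to change.** **Minimum, wording only.** In 7.2 and 11.1, delete the clause that measures the ratio in terms of the primary outcome. State one time horizon for costs and effects. Report incremental cost and incremental QALYs, or net benefit, over that horizon. If utilities stay at six months, label the result a six-month analysis and drop the general value-for-money comparison.

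**Preferred.** Also add EQ-5D to the questionnaires already given at follow-up visits 4, 7, 9 and 11, and name the recurrence treatment recorded under 12.4 as a cost component, so that costs and QALYs cover the same 4.5 years as DFS.

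**Cost.** The wording change is nearly free. The added questionnaire brings a small patient burden, some missing data and no new visits. It needs an amendment approved by the Trial Management Committee and by the ethics committees, and it cannot recover utilities for visits already passed.

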12.0 STUDY VISITS

12.1 PRE-OPERATIVE (VISIT 1)

A cervical biopsy that confirms one of the following cancer types:

Adenocarcinoma

Squamous Cell Carcinoma

Adenosquamous Carcinoma

The following procedures will be performed within six weeks before surgery:

- Chest X-ray (not required in patients with other imaging of the chest);
- CT scan and/or MRI Scan and/or PET Scan and/or Ultrasound of the abdomen and the pelvis,
 if clinically indicated
- 12-lead Electrocardiogram (if indicated);

The following procedures will be performed < 30 days before surgery:

- Sign IRB/HREC-approved written informed consent;
- Collect demographic data, medical history and baseline toxicity data (documented and graded according to CTC Version 3);
- Record all concomitant medications (including prescription, over the counter remedies, vaccination, vitamin, or herbal preparations) used presently and within the past 12 weeks;
- Administer Quality of Life instruments (FACT-Cx, SF12, EQ-5D, MDASI);
- Administer Pelvic Floor Distress Inventory;
- Complete physical and pelvic examination;
- ECOG performance score;
- Weight (kg) and height (cm);
- Standard preoperative laboratory workup as determined by each institution
- Complete Randomization form that verifies the inclusion criteria have been met;
- Complete on-line randomization procedures to randomize the patient and document the result.
- Serum pregnancy test (if clinically indicated)
- E/LFT must include creatinine, bilirubin, albumin, alkaline phosphatase (ALP), aspartate, aminotransferase (AST or SGOT) and alanine aminotransferase (ALT or SGPT)
- Full blood count

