APPENDIX 1: Schedule of Assessments

| Evaluation / Examination | Pre-Op²/ | Surgery | Post-op | | | | |
|-------------------------------------------------|------------------|---------|---------|---------|-----------|-----------|-------------------|
| | Baseline | | 1 week | 6 weeks | 3 monthse | 6 monthse | Follow-uph |
| | Visit 1 | Visit 2 | Visit 3 | Visit 4 | Visit 5 | Visit 6 | |
| Informed Consent | Xa | | | | | | |
| Inclusion/Exclusion Criteria | Xp | | | | | | |
| Medical History | Xa | | | | | | |
| Randomisation | Χb | | | | | | |
| Physical Examination | Хa | | Χg | Х | Х | Х | Xi |
| Height, Weight | Xa | | Хg | Х | Х | Х | |
| ECOG PS | Xa | | Х | Х | Х | Х | |
| Serum pregnancy test | X _{b,c} | | | | | | |
| Concomitant illnesses | Х | | Х | Х | Х | Х | |
| Concomitant medications | Х | | Х | Х | Х | Х | |
| FBC | Xp | | Χg | Xc | Xc | Xc | |
| E/LFT | Xp | | Хg | Xc | Xc | Хс | |
| COAG Profile | X _{b,c} | | | | | | |
| ECG | Xa,c | | | | | | |
| Chest X-Ray (not required in pts with Chest CT) | Хa | | | | | | |
| CT/MRI/PET/USS Abdo & Pelvis | Xa | | | | | | |
| Cervical biopsy/cone biopsy | Хa | | | | | | |
| Clinical staging (EUA) | Xa | | | | | | |
| FACT-Cx | Xp | | Х | Х | Х | Х | F/U 4, 7, 9, & 11 |
| SF-12 | Xp | | Х | Х | Х | Х | |
| EURO-QoL | Xp | | Х | Х | Х | Х | |
| MDASI | Xp | | Х | Х | Х | Х | |
| PFDI | Xp | | | | | Х | F/U 4, 7, 9, & 11 |
| Health Services Questionnaire | | | Х | Х | Х | Х | |
| Demographics of Patients with Cervical Cancer | Xp | | | | | | |
| Surgical Treatment (TLRH/TRRH/ r TARH) | | Х | | | | | |
| Sentinel lymph node biopsy | | Х | | | | | |
| Operative Details | | Х | | | | | |
| Pain Scale (linear analogue scale) | | | Х | Х | Х | Х | |
| | + | | Х | Х | Х | Х | |

a = Within 6 weeks before surgery b = Within 30 days of surgery c = If clinically indicated d = Histologically confirmed cervical cancer e = 3 and 6 months from surgery f = Telephone contact acceptable g = If done, record h = Follow-up visits begin at 9 months post-op & continue every 3 months for 2 years & every 6 months until year 4.5 I = Clinical assessment including an internal exam (see Section 12.4) f = Telephone contact acceptable

g = If done, record h = Follow-up visits begin at 9 months post-op & continue every 3 months for 2 years & every 6 months until year 4.5 I = Clinical assessment including an internal exam (see Section 12 Please note:

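### Baseline questionnaires are timed to surgery and not to randomisation, so this open-label protocol allows them to be completed after the woman knows her arm, which risks bias in patient-reported change scores.

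*Protocol*

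**What the plan says.** Section 5.0 describes the trial as an "open-label, randomized clinical trial design is an equivalence study", so allocation is not concealed from the patient once it is made.

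Section 12.1 (Visit 1) opens its second list with "The following procedures will be performed < 30 days before surgery". That list contains "Administer Quality of Life instruments (FACT-Cx, SF12, EQ-5D, MDASI"), then "Administer Pelvic Floor Distress Inventory", and further down "Complete on-line randomization procedures to randomize the patient and document the result". It gives no order among these items.

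Appendix 1 repeats the window as "b = Within 30 days of surgery" and places the questionnaires and randomisation under the same visit. I read the marker on the questionnaire rows as note b, in line with 12.1.

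Section 7.2 defines the outcome for the four quality-of-life instruments as change "between Baseline (pre-surgery) and 6 months after surgery". Its PFDI entry states no baseline, so the PFDI timing comes from 12.1 and Appendix 1.

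Section 8.0 makes consent and eligibility screening the only preconditions for randomisation. It does not name the questionnaires. Sections 14.1 to 14.3, 15.2 and 15.3 tie completion to visits and do not mention randomisation.

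**The concern.** A baseline is useful because it cannot depend on the allocation. Here it can. A site that randomises on day -28, tells the patient, and hands out the questionnaires on day -1 has followed the protocol.

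Some items could plausibly respond to learning which operation is coming: the FACT-Cx items on nervousness and on fear that treatment will cause bodily harm, the MDASI distress and sleep items (last 24 hours), and the EQ-5D anxiety item (today). If women told they will have open surgery answer worse at baseline, their change to 6 months looks better and a laparoscopic benefit is hidden. The opposite shift would create an apparent difference.

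Section 3.2 ranks quality of life as a highly important endpoint, because survival is expected to be similar. It also reports that in an earlier hysterectomy trial the arms had reached equivalent quality of life by 6 months, the time point used in 7.2. If the true difference is small, a modest baseline shift could dominate the result. Section 11.1 values changes in EQ-5D for the QALYs, so the cost-utility result is exposed if it uses that baseline.

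**Working it through.** **1. Is the bullet order a safeguard?** The questionnaires stand above the randomisation bullet in 12.1. Below that bullet come the serum pregnancy test, the full blood count, and this item: "E/LFT must include creatinine, bilirubin, albumin, alkaline phosphatase (ALP), aspartate, aminotransferase (AST or SGOT"). White cells, platelets, creatinine, bilirubin, transaminases and a negative pregnancy test are inclusion criteria (section 4.1, items 4.1 to 4.4 and 10), and section 8.0 requires eligibility to be screened before randomisation. Read as a strict sequence, the list would contradict section 8.0, so its order cannot be relied on as a rule.

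**2. Size of the bias.** The plan has no figure to reproduce here. The following is an illustration.

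Inputs:
- n = 370 per arm (section 9.0), with complete data assumed.
- d = difference between arms in mean baseline caused by knowing the allocation, in SD units. Assumed.
- r = correlation of baseline with follow-up. Assumed, 0.3 to 0.7.
- Equal SDs, no true treatment effect, two-sided 5% test, normal approximation.

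Formulas (absolute bias; its sign is opposite to the shift):
- Change score: bias = d, SE = √(2(1 − r)) × √(2/n).
- Baseline-adjusted: the adjusted difference subtracts slope × baseline difference, and the slope is r, so bias = r × d, SE = √(1 − r²) × √(2/n).
- Follow-up score alone: bias = 0.
- Rejection rate = P(|Z + bias/SE| > 1.96).

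Worked case, r = 0.5 and d = 0.1, with √(2/370) = 0.0735:
- Change score: SE = 1 × 0.0735; 0.1/0.0735 = 1.36; rejection 27.5%.
- Adjusted: bias 0.05; SE = 0.866 × 0.0735 = 0.0637; 0.05/0.0637 = 0.785; rejection 12.3%.

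| d (SD) | r | Change-score bias | Rejection | Adjusted bias | Rejection |
|---|---|---|---|---|---|
| 0 | any | 0 | 5% | 0 | 5% |
| 0.1 | 0.3 | 0.10 | 21.0% | 0.03 | 7.1% |
| 0.1 | 0.5 | 0.10 | 27.5% | 0.05 | 12.3% |
| 0.1 | 0.7 | 0.10 | 41.9% | 0.07 | 26.6% |
| 0.2 | 0.3 | 0.20 | 63.3% | 0.06 | 13.7% |
| 0.2 | 0.5 | 0.20 | 77.6% | 0.10 | 34.9% |
| 0.2 | 0.7 | 0.20 | 94.0% | 0.14 | 76.0% |

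With 50 per arm (the Stage 1 cohort) and d = 0.1, the bias is the same but the noise is larger: rejection is 7.1% to 9.9% for change scores and 5.3% to 7.8% with adjustment.

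**3. What d means.** It is an average over the whole arm. If only a fraction p of one arm answers late and each of those women shifts by s, then d = p × s. A quarter answering late with s = 0.4 SD gives 0.25 × 0.4 = 0.1 SD; with s = 0.15 SD it gives 0.25 × 0.15 ≈ 0.04 SD. If both arms shift equally, d = 0.

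**4. With the forms completed before randomisation,** d = 0 by design and all three analyses keep their 5% level.

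**The case against.** The best defence is that 12.1 reads naturally as questionnaires first. Consent, history, quality-of-life forms and PFDI come before the Randomization form and the on-line step, all within Visit 1. The laboratory bullets at the end can be read as detail of the preoperative workup listed earlier. This is fair as a guess at usual practice, and many sites may work that way. It does not make the order a requirement, and the only stated baseline rule, in 7.2, is before surgery.

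The mechanism also varies by instrument. The PFDI asks about bladder, bowel and prolapse symptoms over 3 months, and most SF-12 items cover four weeks, so much of their recall can precede allocation. This stands: the risk is most plausible for short-recall mood, worry and anxiety items.

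The planned analysis may lean less on baseline than 7.2 suggests. Section 10.2 describes scores by arm at each assessment and does not choose between change scores and baseline adjustment. That choice may lie in a statistical analysis plan that was not available. The economic component is optional for sites (section 11.0). These points limit the exposure but do not remove it while 7.2 defines the outcome as change from baseline.

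Detection is partly possible now. The FACT-Cx, MDASI, SF-12 and PFDI forms in Appendix 6 carry a visit date, which can be set against the randomisation record. I found no date on the EQ-5D form as reproduced, although the layout may have lost it.

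A reader might infer that every change-from-baseline outcome in the trial is biased. The documents do not support that. Late completion is permitted but not scheduled, bias also needs a shift that differs by arm, and haemoglobin change is a laboratory value that this mechanism does not touch.

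**Conclusion.** The gap in the protocol is real. Its consequence is a risk of bias, not a demonstrated bias. It concerns the patient-reported change outcomes and any QALY calculation that uses the EQ-5D baseline. The primary outcome is not touched.

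The size cannot be fixed from the documents, since both d and r are assumptions. Even a small shift would matter at the full sample size, above all for unadjusted change scores. A reader might also infer that adjustment for baseline is useless, or that a shift of 0.15 SD would by itself make a result significant. Neither follows. Adjustment reduces the bias to r × d without removing it. At r = 0.5 a shift of 0.15 SD gives 0.15/0.0735 = 2.04 standard errors for a change score, which is about a 53% chance of significance.

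This is a free or cheap improvement. It belongs in the protocol because no later analysis can recover a baseline that was not taken before the allocation was known.

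**What to change.** - Sections 12.1 and 8.0 and Appendix 1: state that the baseline FACT-Cx, SF-12, EQ-5D, MDASI and PFDI are completed after consent and before on-line randomisation.
- Section 7.2: define the quality-of-life baseline as pre-randomisation instead of pre-surgery.
- Randomization form: add the questionnaire completion date as a required field.
- Women already enrolled: compare completion dates with randomisation dates, report how many baselines were late in each arm, and run a sensitivity analysis that excludes them.

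The cost is a sentence in three places, one changed word in 7.2, one date field and a little site discipline. Section 14.0 puts the quality-of-life surveys at under 20 minutes, and all five instruments already belong to Visit 1, so no visit is added.
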